7.2.3 Day 1 Visit

See Table 2 for the procedures and assessment to be performed during the Day 1 visit of the study. The Day 1 visit will occur after all baseline tests are completed and it has been determined that the subject remains eligible. Once the subject is deemed eligible to continue in the study the subject will be administered the investigational product.

7.2.4 Week 2 Visit

See Table 2 for the procedures and assessment to be performed for week 2 through month 6 visit of the study. Outpatient visits should be completed as close to the scheduled visit dates as possible. There will be a +/- window of 2 days for the week 2 study visits.

7.2.5 Month 1 – Month 6 Visits

See Table 2 for the procedures and assessment to be performed for week 2 through month 6 visit of the study. Outpatient visits should be completed as close to the scheduled visit dates as possible. There will be a +/- window of 2 weeks for the Month 1 through month 6 study visits.

7.2.6 Month 12 Visit

See Table 2 for the procedures and assessments to be performed for Month 12 visit. This visit will be conducted via a phone interview with the subject. A phone script will be

provided to the study personnel to use when interviewing the subject. There will be a +/- window of 2 weeks for this visit. All fifteen (15) pilot phase subjects will be informed with the option of having additional administrations of allogeneic hMSCs at this visit.

7.2.7 Biomarker Assessment

All samples will be identified so that they can be linked to individual subjects. These samples may be stored indefinitely. Individual results will not be returned to the subject or the study physician. The samples will be linked to subjects, but there will be no recontact. Data presented in publications will not contain individual subjects' clinical characteristics or outcomes; only aggregate data from the entire study will be disclosed.

7.2.8 Immune Monitoring for Graft Rejection

The studies planned in the CRATUS protocol will utilize allogeneic mesenchymal stem cells (MSC) in subjects with frailty syndrome. The use of an allogeneic graft raises the potential of graft rejection through immune cells resulting in failure of the therapy. MSCs are ideal candidates for allogeneic transplantation because they show minimal MHC class II and ICAM expression and lack B-7 co-stimulatory molecules necessary for T-cell mediated immune responses^{57, 58}. Indeed MSCs do not stimulate a proliferative response from alloreactive T-cells even when the MSCs have differentiated into other lineages or are exposed to proinflammatory cytokines. Previous studies have demonstrated that MSCs have significant immunomodulatory effects, inhibiting T-cell proliferation, prolonging skin allograft survival, and decreasing graft-versus-host disease (GVHD). Recently human MSCs were shown to alter the cytokine secretion profile of dendritic cells, T cells, and natural killer cells in vitro, inhibiting secretion of proinflammatory cytokines (e.g. TNF- α , IFN- γ) and increasing expression of suppressive cytokines (e.g. IL-10), possibly via a prostaglandin E2 mediated pathway.

In vivo studies of the fate of MSCs have shown that, when transplanted into fetal sheep, human MSCs engraft, undergo site-specific differentiation into various cell types, including myocytes and cardiomyocytes and persist in multiple tissues for as long as 13 months after transplantation in non-immunosuppressed immunocompetent hosts. Further, in vivo studies using rodents, dogs, goats, and baboons demonstrate that allogeneic MSCs can be engrafted into these species without stimulating systemic alloantibody production or eliciting a proliferative response from recipient lymphocytes. These findings, coupled with our demonstration of efficacy of these cells for cardiac repair, solidify the notion of using MSCs as an allograft for successful tissue regeneration.

As part of the CRATUS protocol we will obtain peripheral blood samples from all subjects to evaluate the panel reactive antibodies (PRA) as well as the presence of activated T cells. Two heparinized (green top) vacutainer tubes (approx. 15 cc total blood) will be collected at different time points during the study: at day one prior to infusion of MSC and visits through month 6. Peripheral blood mononuclear cells (PBMC) will be isolated from heparinized blood by ficoll sedimentation and will be viably cryopreserved for planned assessments of T cell activation.

Two of the best-accepted markers of T cell activation are CD69 and CD25 (IL-2 receptor α). We will monitor the activation of T cells by flow cytometric analysis of CD3+CD25+CD69+ cells in thawed PBMC. CD69 is an immediate/early marker of CD3+ T cell activation while CD25 expression increases within 1-2 days of activation and remains sustained over the intermediate-long term during chronic immune activation. Given the differences in the kinetics of CD69 and CD25 up regulation, assessment of both activation phenotypes (CD3+CD69+ and CD3+CD25+) will maximize the sensitivity of detection of T cell activation following autologous or allogeneic MSC infusion.

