- **Cell-surface markers:** CD19, CD27, IgD, and CD5 (for Switched Memory, Naïve, Late/Exhausted, IgM memory B cells and regulatory B cells); CD19 and intracellular TNF- α (to assess intracellular TNF- α); CD3, CD4, CD8, CCR7 and CD45RA (for Central Memory, Naïve, Effector Memory, TEMRA T cells and CD4 to CD8 ratio); CD3, CD25 and FOXP3 (to assess regulatory T cells)
- **Transcriptomic/Proteome:** RNA, miRNA, protein samples, and telomerase, akt
- **Growth factors:** Sdf-1, notch,
- **Functional Assays:** cell growth rate, VEGF, and CFU assay

4 – Immune monitoring for graft rejection. Calculated panel reactive antibodies will be performed from the serum of the subjects on day 1 and 6 months post treatment. In addition, the following cell surface markers will be used to assess for activated T-cells based upon a CD3 $^+$ CD25 $^+$ (late/chronic T cell activation) or CD3 $^+$ CD69 $^+$ phenotype (early T cell activation).

5 – Optional brachial ultrasound to assess endothelial function.

6 – Optional: An additional 5 lavender top tubes (EDTA) will be drawn to assess the ability of endothelial progenitor cells to form colonies.

7 – 4 meter gait speed test will be performed twice per visit and the average of the exams will be taken.

8 – DEXA scan will be performed at baseline and Month 6. The scans of the hip and spine for bone density, and total body composition will be assessed at both visits.

9 – Subject and Physician Global Assessments are not applicable to pilot subjects in the initial infusion of the trial.

10 – Dynamometer will be performed at least three (3) times during each applicable visit for each hand. The three values collected will be averaged for each hand. (Please reference the instruction manual on how to administer.)

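### Immune monitoring has no post-infusion sample before Day 12 (Day 16 in the addenda) and does not separate CD25+ activation from regulatory T cells at the middle visits, so it supports a narrower conclusion than section 7.2.8 claims.

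*Combined protocol and SAP*

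**What the plan says.** Section 7.2.8 draws blood "at day one prior to infusion of MSC and visits through month 6". It describes CD69 and CD25 by their onset: "CD69 is an immediate/early marker of CD3+ T cell activation while CD25 expression increases within 1-2 days of activation". It adds that CD25 "remains sustained over the intermediate-long term during chronic immune activation". From this difference in timing it concludes that assessing both phenotypes gives the greatest sensitivity for detecting T cell activation after infusion.

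The analysis is first described as "flow cytometric analysis of CD3+CD25+CD69+ cells in thawed PBMC". Two sentences later the same section names two separate phenotypes, CD3+CD69+ and CD3+CD25+. Key 4 of Table 2 also uses the two phenotypes, joined by *or*, and labels CD3+CD25+ as "late/chronic T cell activation".

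Key 3 of the same table defines a biomarker panel that includes "CD3, CD25 and FOXP3 (to assess regulatory T cells". Keys 3 and 4 recur with the same marker definitions in Tables A1, B1, C1 and D1.

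The first visit after infusion in the main study is Week 2, for which section 7.2.4 states: "There will be a +/- window of 2 days for the week 2 study visits". The addenda have no Week 2 visit. Their first post-infusion visit is Month 1, Day 30 with a window of 2 weeks either way.

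**The concern.** A marker chosen because it responds at once is informative about the response to infusion only if blood is taken soon afterwards. Here it is not. A low CD69 reading at Week 2 or Month 1 could be reported as showing no T cell activation, when the early period was never observed.

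The CD25 reading has a different weakness. If regulatory cells carry CD25, as key 3 says, a rise in CD3+CD25+ cells could be effector activation, a regulatory response, or both. The plan describes mesenchymal cells as immunosuppressive (A.2) and as increasing suppressive cytokines (7.2.8), so a regulatory rise is plausible on its own rationale.

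The stakes are highest in Addendum C, where immunologic safety of repeated infusions is a primary objective (C.3.1.1). C.1 already cites the absence of significant immunologic reactions among its grounds for further infusions. In the main study and Addenda A, B and D, cPRA is scheduled only on Day 1 and at Month 6, so between those visits T cell phenotyping is the only specified rejection readout.

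**Working it through.** The plan gives no sample size, threshold or error rate for this assay, so there is no figure to reproduce. The check is visit-window arithmetic and a comparison of definitions.

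**1. Earliest and latest first post-infusion draw** (nominal day minus and plus the window)

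- Pilot and randomized phases, Week 2: 14 − 2 = Day 12; 14 + 2 = Day 16.
- Addenda A to D, Month 1: 30 − 14 = Day 16; 30 + 14 = Day 44.

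The plan's own onset times are immediate or early for CD69 and 1 to 2 days for CD25. No post-infusion draw falls near either onset. The only earlier sample is the Day 1 pre-infusion baseline.

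**2. Which draws can separate regulatory cells** (from the immune-monitoring and biomarker rows of the schedules, and key 4)

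| Draw | Main study | Addenda | CD3/CD25/FOXP3 panel | cPRA |
|---|---|---|---|---|
| Day 1 | yes | yes | yes | all phases |
| Week 2 | yes | no visit | no | no |
| Month 1 | yes | yes | no | Addendum C only |
| Month 3 | yes | yes | no | Addendum C only |
| Month 6 | yes | yes | yes | all phases |

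The FOXP3 panel coincides with immune monitoring at 2 of 5 draws in the main study and 2 of 4 in the addenda. Nothing scheduled separates the two cell types at Week 2, Month 1 and Month 3.

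**3. Overlap of keys 3 and 4**

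CD3+CD25+ = (CD3+CD25+FOXP3−) + (CD3+CD25+FOXP3+). Key 4 counts the whole left-hand side as late or chronic activation. Key 3 treats the last term as regulatory. A change in the total does not show which term moved.

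**4. The two gates in 7.2.8**

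The triple-positive set is the intersection of the two phenotypes, so

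n(CD3+CD25+CD69+) ≤ min[ n(CD3+CD25+), n(CD3+CD69+) ].

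It cannot count more cells than either marker alone, so it works against the stated aim of sensitivity. It also excludes any late-activated cell that carries CD25 without CD69. Under that gate the overlap in step 3 shrinks to CD69+ regulatory cells, so the choice of gate also changes what the result means.

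**The case against.** The case for leaving the plan alone has real substance.

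- **CD69 is not the only readout.** CD25 is described as sustained and is the marker suited to Week 2 through Month 6. Antibodies are measured too, and Addendum C, where immunologic safety is a primary objective, runs cPRA at Day 1 and Months 1, 3 and 6. This stands: a lasting response could still be detected.
- **Late CD69 may still carry information.** The plan gives no time for which CD69 stays raised. Section 7.2.8 cites persistence of human cells for as long as 13 months in an animal model. If donor cells persist, new activation could occur at any visit. This stands against any claim that late CD69 is worthless or that rejection would be missed. It does not make a Day 12 sample informative about the first days.
- **There are controls.** Each subject has a baseline and the randomized phase has placebo. These handle background CD25+ cells. They cannot say whether a rise caused by treatment is activation or regulation, and the addenda have no concurrent placebo.
- **The assay is exploratory in the main study.** T cell activation is not among its endpoints, safety variables or stopping guidelines. This limits the weight of the point there, but less so in Addendum C.
- **The two-phenotype gate is already in 7.2.8.** True, so that part is a reconciliation within the section.

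A reader might go further and infer that the monitoring would falsely signal rejection. The documents do not support that. No positivity threshold or rejection rule exists to be falsely triggered, and no passage says that these cells raise regulatory T cells. Nor do the documents give a FOXP3-positive share, so the size of the overlap cannot be estimated from them.

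**Conclusion.** The point holds as a limit on interpretation.

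- Early activation after infusion is unobserved until at least Day 12 in the main study and Day 16 in the addenda. The sensitivity claim in 7.2.8 is therefore unsupported for that period. This rests only on the visit windows and the onset times that the plan states.
- A CD3+CD25+ rise cannot be told apart from a regulatory response at 3 of 5 main-phase draws and 2 of 4 addendum draws. At Day 1 and Month 6 it could be, but key 4 does not call for the split.
- The two gates in 7.2.8 conflict, and the triple-positive one cannot be the more sensitive.

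It would be too strong to say that the monitoring depends on CD69, that there is no sample at all before Day 12, or that rejection would be missed. The plan pairs CD69 with CD25 and cPRA, takes a Day 1 baseline, and gives no CD69 persistence time. The main study's primary endpoint is unaffected. The consequence is greatest for the immunologic objective of Addendum C, where the added cPRA visits partly compensate.

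**What to change.** 1. In section 7.2.8, replace the triple-positive description with CD3+CD69+ and CD3+CD25+ analysed separately, matching key 4 of every table.
2. At Day 1 and Month 6, where CD3, CD25 and FOXP3 are already measured, report CD3+CD25+ as FOXP3-negative and FOXP3-positive alongside the total. At the other visits, interpret a CD25 rise as non-specific unless FOXP3 is added to stored cells. That addition should be optional, where cells allow: the plan says that PBMC are viably cryopreserved but gives no cell yield and does not say what remains from cohorts already treated.
3. State in 7.2.8 that CD69 from Day 12 on (Day 16 in the addenda) is not evidence against early activation, and limit the sensitivity claim accordingly. Rest the immune-safety conclusion on CD25, with the FOXP3 split, and on cPRA.

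The cost is wording, a little more analysis of data already planned, and a narrower immunologic claim. No new visit or blood draw is needed. The early period stays unobserved, and the report should say so.

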8. SAFETY

8.1 Safety Variables

1. Vital signs
2. Physical examination
3. Clinical laboratory tests
4. Adverse events

8.2 Laboratory Evaluations

At screening, the HIV-1 and HIV-2 tests, CMV, hepatitis screen and β -HCG serum pregnancy tests (only for women of child bearing potential) will be performed locally at the study site. Laboratory safety tests will consist of the following:

Serum chemistry: sodium, potassium, chloride, carbon dioxide, BUN, creatinine, glucose, calcium, phosphate, AST/SGOT, ALT/SGPT, total bilirubin (fractionate if total >1.5 times normal), alkaline phosphatase, albumin, fibrinogen, IL6, D-Dimer, Coagulation studies

Hematology (CBC): hemoglobin, hematocrit, platelets, WBC, WBC differential

The Investigator will review all clinically relevant laboratory results requested in the protocol. The diagnosis associated with any clinically significant laboratory deviations should be recorded as an AE and should indicate the underlying abnormality or diagnosis (such as renal insufficiency) as opposed to the observed deviation in laboratory results (such as elevated creatinine). If there is no underlying abnormality linked to a clinically significant abnormal laboratory value, the observed deviation should be reported as the AE.

8.2.1 Pulse Oximetry

Pulse oximetry will be used to observe oxygen saturation when measuring vital signs at screening. Pulse oximetry will also be used throughout infusions and 2 hours following infusions. Subjects requiring oxygen, need the peripheral artery oxygen saturation (SaO_2) to be $\geq 93\%$ when given a maximum of 2L/minute supplemental O_2 via nasal

cannula. Infusion toxicity will be assessed based on decreases in oxygen saturation during infusion. The infusion will be stopped if the oxygen saturation does not return to >93% within 3 minutes of initiating supplemental oxygen or if the subject requires greater than 2L/min supplemental oxygen to achieve the required saturation of >93%. If this occurs then subjects will be admitted to the hospital for observation.

8.2.2 Pregnancy

There is no information allogeneic hMSCs and its effects or potential risks to a fetus or unborn child. The Principal Investigator and DSMB must be notified within twenty-four hours of investigator's awareness of the pregnancy via facsimile if a study subject becomes pregnant during the study. Males and females of childbearing potential ≥ 60 to ≤ 95 years of age at the time of signing the Informed Consent Form with documented FRAILTY must practice any one of the enumerated forms of contraception. Items will be acceptable for meeting the studies contraceptive requirements as listed in section 8.2.2. Females will be defined as non-childbearing potential if surgically sterilized (i.e. bilateral tubal ligation, bilateral oophorectomy, or complete hysterectomy) or post-menopausal (defined as 12 months no menses with an alternative medical cause and with a follicle stimulating hormone (FSH ≥ 25.8 mIU/mL). Non-sterilized males who are sexually active with a female partner of childbearing potential must use any one of the enumerated contraceptive items as listed in section 8.2.2 throughout the study.

Acceptable forms of contraception include: 1) abstinence, 2) condoms (male or female) with a spermicidal agent, 3) diaphragm or cervical cap with spermicidal agent, 4) intrauterine device (IUD), 5) oral contraceptive, 6) injectable or transdermal hormonal contraceptive, 7) successful vasectomy with resulting azoospermia or azoospermia for any other reason, and 8) hysterectomy, bilateral oophorectomy, or tubal ligation.

Prior to study enrollment, women of childbearing potential must be advised of the importance of avoiding pregnancy during trial participation and the potential risk factors for a pregnancy. The subject must sign an informed consent and written authorization for use and disclosure of PHI document stating that the above-mentioned risk factors and the consequences were discussed with her.

8.2.3 Determination of Infusional Toxicity

Infusional toxicity will be evaluated by continuously monitoring the subject's vital signs and O₂ saturation by pulse oximetry from the time of allogeneic hMSCs administration until two hours after infusion is complete. Since there is no specific or antidotal therapy for AEs arising from allogeneic hMSCs, any toxicity that may arise during a subject's participation in this study should be managed with supportive measures at the discretion of the treating physician.

8.2.4 Subject Stopping Guidelines

This guideline is to be used to indicate boundaries requiring discussion by the Data and Safety Monitoring Board (DSMB) and is designed to assist the independent DSMB in overseeing the study. The DSMB may also request additional interim analyses and develop other criteria including provision for monitoring of potential late effects to determine when to intervene in the enrollment or treatment of subjects in the study. The first more conservative stopping guideline is to monitor subjects for unexpected SAEs where there is a reasonable possibility that the study product or administration procedure caused the event within 30 days of administration including subject death, grade 3 myocardial infarction, or grade 3 hemodynamically unstable ventricular tachycardia. Study accrual and further treatment of subjects will be put on hold if any subjects experience one of these events. The DSMB will be notified within 24 hours of the occurrence of these events and will be convened within 3 business days to review the event and study.

The following are subject stopping guidelines:

1. Any subject who develops persistent (that is, still existing more than 3 hours after the end of IP infusion) cardiorespiratory signs or symptoms (for example, shortness of breath, tachypnea, tachycardia, hypotension, or palpitations) will continue with all scheduled follow-up if such follow-up is considered safe in the opinion of the Investigator. A subject may still be able to receive additional infusions, based on the investigator's judgement.
2. Any subject whose infusion is stopped due to cardiorespiratory distress will not receive further IP infusions until it is considered safe in the opinion of the Investigator, but subjects will continue with all scheduled follow-up if such follow-up is considered safe. A subject may still be able to receive additional infusions, based on the investigator's judgement.
3. The proportion of subjects experiencing TE-SAE as defined in Section 2.2.1 will be monitored within 30 days of infusion. This guideline is designed to assist the independent DSMB in overseeing the study and indicate boundaries needing discussion by the DSMB. The DSMB may also request additional interim analyses and develop other criteria including provision for monitoring of potential late effects to determine when to intervene in the enrollment or treatment of subjects in the study.
4. Monitoring of key safety endpoints will be conducted (Please reference section 2.2.1). If rates significantly exceed the pre-set threshold, then the DSMB will be advised.

The stopping guidelines serve as a mechanism for consultation with the DSMB for additional review, and are not formal "stopping rules" that would mandate automatic closure of study enrollment. It is designed to assist the independent DSMB in

overseeing the study. The DSMB may also request additional interim analyses and develop other criteria including provision for monitoring of potential late effects to determine when to intervene in the enrollment or treatment of subjects in the study.

8.2.5 Subject observation and discontinuation after IP administration

The IP administration guidelines in **Appendix 1** list the study requirements for subject observation and discharge after IP administration.

8.3 Definition of an Adverse Event

An Adverse Event (AE) is any untoward medical occurrence in a subject or clinical investigation subject temporally associated with the use of a medicinal product, whether or not considered related to the medicinal product. The occurrence does not necessarily have to have a causal relationship to the treatment received in the study. An AE can therefore be any unfavorable and unintended sign (including an abnormal laboratory finding, for example), symptom, or disease (new or exacerbated) temporally associated with the use of a medicinal product, whether or not considered related to the medicinal product.

Examples of an AE include:

1. Exacerbation of a chronic or intermittent pre-existing condition including either an increase in frequency or intensity of the condition.
2. Significant or unexpected worsening or exacerbation of the condition/indication under study.
3. A new condition detected or diagnosed after study therapy administration even though it may have been present prior to the start of the study.
4. Pre- or post-treatment events that occur as a result of protocol-mandated procedures (e.g., invasive protocol-defined procedures, modification of a subject's previous treatment regimen).

An AE does **not** include:

1. Medical or surgical procedures (e.g., colonoscopy, biopsy). The medical condition that leads to the procedure is an AE.
2. Social or convenience hospital admissions where an untoward medical occurrence did not occur.
3. Day to day fluctuations of pre-existing disease or conditions present or detected at the start of the study that do not worsen.

4. The disease/disorder being studied or expected progression, signs, or symptoms of the disease/disorder being studied unless more severe than expected for the subject's condition.

